7.1. Demographics and baseline characteristics

Quantitative variables will be summarized using the number of subjects (N), mean, SD, median, 25th and 75th percentiles, and minimum and maximum. Qualitative variables will be summarized using counts and percentages.

The following demographic and baseline characteristics will be summarized: age, gender, height, weight, ethnicity, and past use of statin. Blood pressure and selected biochemistry laboratory measurements reported as well.

Age in years will be calculated as the integer portion of the following:

$$[(\text{Date of randomization} - \text{Date of birth}) + 1] / 365.25.$$

Unless otherwise stated, percentages will be calculated relative to the number of subjects randomized.

7.2. Concomitant medications

Information on concomitant medication may be summarized by generic name as reported on the concomitant medication CRF. The number and percentage of subjects who took at least one drug within each generic type will be presented. Subjects will be counted only once if they take the same generic medication more than once.

7.3. Medical history

Medical history will be coded using the MedDRA and summarized by system organ class (SOC) and preferred term (PT). Medical history may be sorted by descending overall frequency, by SOC and PT, in the summary tables.

8. Protocol deviations

Important protocol deviations will be summarized by the category reported on the CRF form and sorted by descending overall frequency

9. Adverse events

Adverse events (AEs) are monitored throughout the study and documented on the appropriate AE form. They are coded using the MedDRA dictionary by system organ class (SOC) and preferred term (PT); they will be classified by seriousness, severity, and relation to study medications.

AEs will be summarized by subject, not event. AE data will be also presented in listings.

10. Quality of life measures and confounding life events

Each month participants fill out the following two validated questionnaires related to the impact of their side-effects on their quality of life: EuroQol (EQ-5D-3L) and the side effects domain of the Treatment Satisfaction Questionnaire for Medicine (TSQM) questionnaire.

Participants will also fill in a short questionnaire detailing any potentially confounding life events they experienced over the previous month (e.g., change of daily routine, holidays, bereavement). At the end of study visit participants will have an exit interview exploring the nature of symptoms occurring during the study in case they may differ from those described in the baseline interview.

The daily quality of life scores will have their distribution described by the mean and standard deviation or, if not normally distributed, by the median and interquartile range. These scores will then be aggregated to monthly average scores. The correlation within group and intraclass correlation will be used to assess within-subject agreement and group mean reliability. To establish the measurement properties (i.e., convergent validity and measurement invariance) of the new measure we will examine the correlations between the month averages and each of the two monthly validated scoring systems (EQ-5D-3L and TQSM). A strong correlation ($r>0.4$) will reflect satisfactory convergent validity. The stability of the correlations across the 12 months will reflect the degree of measurement invariance. We will test this formally by a pair of path analysis models using *Mplus*: one model in which the within-time correlations between the monthly aggregate of the new measure and the validated measure (i.e. EQ-5D-3L and TQSM) are fixed across time, and another where they are allowed to differ. If the latter model does not offer a significant improvement in model fit (assessed by chi-squared and fit indices), this suggests measurement invariance.

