3 STUDY DESIGN

3.1 PRE-RANDOMISATION EVALUATIONS

A participant and public involvement group have already provided feedback to assist the development of the study proposal. Their feedback is summarised in Appendix 1. The phone application has also been piloted among healthy volunteers and feedback summarized in appendix 2.

3.2 PILOT STUDY: SEMI-STRUCTURED INTERVIEW TO EXPLORE AND MEASURE SYMPTOM EXPERIENCE TO REFINE MEASUREMENT TOOLS FOR THE MAIN TRIAL

Participants: Prior to the trial we will recruit 20 participants who are either 1) currently taking statins with and without adverse symptoms or 2) have previously ceased statin therapy due to adverse symptoms.

Method: The interviews will have two parts. Firstly, we will conduct a brief interview to explore individuals' current or past experience of statins. Secondly, participants will fill out a structured questionnaire that assesses the intensity within each participant of several commonly described statin side-effects, each on a scale of 0-100. These would include muscle aches, fatigue, headache, and gastrointestinal symptoms. In addition, the participants will be asked to complete and comment on the daily and monthly questionnaires planned for the main trial to assess their appropriateness. At the same session participants will have a cognitive interviews to determine their reasoning whilst filling out various different scales. The interviews will be audio-recorded and transcribed using Nvivo software. The exploratory part of the interviews will be interpreted using thematic analysis³² and the cognitive interviews using a content analysis approach³³.

Confidential Page 6 of 22

SAMSON Protocol No: 1.4

Version 1.4 10th April 2020

Scale refinement: The scales used in the main trial will be refined based on the findings from the interviews, and any modifications piloted among further participants.

3.3 RANDOMISED CONTROLLED TRIAL: EVALUATING IN A COHORT OF PARTICIPANTS THE PROPORTION OF ADVERSE SYMPTOMS TRULY DUE TO THE STATIN RATHER THAN THE NOCEBO EFFECT

Participants: 50 participants will be recruited to the trial.

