3.4 STUDY OUTCOME MEASURES

For the trial, each participant will receive a smartphone or if preferred can have the application downloaded to their existing phone to allow real-time daily documentation of symptoms experienced on a visual analogue scale of 0-100. Example screen-shots (which will be further refined based on the findings from the pilot study) are shown in Appendix 3. Participants will receive training on the simple touch-screen interface and a leaflet with further information will also be provided. An optional daily reminder can be setup on the participants' phones. Participants will rate symptoms every day, with the daily scores aggregated into a monthly score. This is preferable over scoring only once a month, because participants may struggle to remember and aggregate their symptom burden especially if it varies between days.

Confidential Page 7 of 22

SAMSON Protocol No: 1.4

Version 1.4 10th April 2020

Each month participants will fill out two validated questionnaires on the impact of their side-effects on their quality of life. These are EuroQol (EQ-5D-3L), ³⁴ a well-validated measure of health related quality of life, and the Treatment Satisfaction Questionnaire for Medicine (TSQM) questionnaire, a validated treatment satisfaction questionnaire. EQ-5D-3L assesses five domains of health and overall self-rated health using a visual analogue scale. EQ-5D-3L is conventional for assessing efficacy of medication on quality of life but may not be sufficient for assessing side effects, ³⁵ therefore the TSQM questionnaire will also be used. Use of both a health related quality of life questionnaire and a treatment satisfaction questionnaire will allow assessment of participants' multiple health states, overall self-rated health status and treatment satisfaction, and provide a test of both convergent validity and measurement invariance for the monthly aggregate symptom burden score.

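### The convergent-validity rule in SAP section 10 appears to use same-month correlations across participants, which cannot show that the symptom score tracks change within a person, and its signed cut-off comes without scale directions

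*SAP*

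**What the plan says.** SAP section 10 averages the daily scores by month and then states that "we will examine the correlations between the month averages and each of the two monthly validated scoring systems", namely EQ-5D-3L and the TSQM. The criterion is "A strong correlation ($r>0.4$) will reflect satisfactory convergent validity". No absolute value, expected sign, confidence interval or rule for combining the months is given.

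Two further statements bear on the level of these correlations. One is "The stability of the correlations across the 12 months will reflect the degree of measurement invariance". The other is the formal test, which compares path models in which "the within-time correlations between the monthly aggregate of the new measure and the validated measure" are either held equal over time or left free.

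The one statistic in that section described as within-subject serves a different purpose: "The correlation within group and intraclass correlation will be used to assess within-subject agreement and group mean reliability". It concerns the daily scores themselves, not their relation to the questionnaires.

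On what the scales are:
- Protocol section 3.4 calls the new measure a monthly symptom burden score, and SAP section 6.1 describes a 0-100 symptom scale.
- SAP section 10 and the screenshot captions in Protocol Appendix 3 call the daily scale quality of life.
- For the comparator, Protocol section 3.4 says "EQ-5D-3L assesses five domains of health and overall self-rated health using a visual analogue scale", without saying which of these outputs is to be correlated.
- SAP section 10 narrows the TSQM to its side-effects domain.

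**The concern.** The trial needs a score that moves when a given person's symptoms move. The first objective is a method that works for the individual. The SAP primary endpoint (section 6.1) is a per-participant ratio: placebo minus no tablet, over statin minus no tablet. Participants are shown their own result at the end of the study (Protocol section 3.4).

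A correlation across participants within one month largely answers another question, namely whether people who generally report more symptoms also report a generally different health state. A score can do well on that and still fail to follow change, or the reverse. At stake is the validity claim for the new score: it could be called satisfactory, or not, on evidence that does not isolate the property the endpoint uses.

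A second, smaller matter is that a signed cut-off cannot be applied safely until the direction of each scale is fixed.

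**Working it through.** **Inputs.** From the documents: cut-off 0.4 and 12 months (SAP section 10); 50 participants planned and 60 randomised (SAP section 4.1). The 0.4 is a fixed rule, so there is no derived figure to reproduce. The documents give no between-person variance share (s), between-person correlation (r_b) or within-person correlation (r_w). All values of these below are assumptions.

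**Step 1: level of the planned correlation.** A separate correlation for each of 12 months, checked for stability over months, can be computed only across participants, because each person contributes one pair of values per month. This is an inference; the convergent-validity sentence itself does not state the level.

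**Step 2: what the endpoint uses.** Add a constant a to all of one person's scores. Then (placebo + a) − (no tablet + a) = placebo − no tablet, and likewise for statin. The person's stable level cancels from numerator and denominator. Only within-person differences remain.

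**Step 3: what a same-month correlation contains.** With person effects and independent monthly deviations,

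r_month = √(s_x·s_y)·r_b + √((1−s_x)(1−s_y))·r_w,

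which for equal shares is s·r_b + (1−s)·r_w.

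**Step 4: a score that does not track change** (r_b = 0.8, r_w = 0, scales aligned).

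| Share s | r_month = 0.8·s | Against 0.4 |
|---|---|---|
| 0.3 | 0.24 | fails |
| 0.5 | 0.40 | borderline |
| 0.7 | 0.56 | passes |
| 0.8 | 0.64 | passes |

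The break-even share is 0.4/0.8 = 0.50. With r_b = 0.7 it is 0.4/0.7 = 0.57.

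**Step 5: a score that tracks change well** (r_b = 0.2, r_w = 0.8).
- s = 0.7: 0.7 × 0.2 + 0.3 × 0.8 = 0.14 + 0.24 = 0.38, a narrow miss.
- s = 0.5: 0.10 + 0.40 = 0.50, a pass.
- Break-even: 0.8 − 0.6·s = 0.4 gives s = 0.67.

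**Step 6: simulation check** (50 people, 12 months, 2,000 runs, s = 0.7). Passing was taken to mean that the average of the 12 monthly correlations exceeds 0.4; the SAP does not say how the months are combined, so this too is an assumption.
- Step 4 score: mean monthly r 0.56, mean within-person r 0.00, passes in 98% of runs.
- Step 5 score: mean monthly r 0.38, mean within-person r 0.80, passes in 42% of runs.

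**Step 7: precision.** By Fisher's z, one observed monthly r of 0.40 has a 95% interval of 0.14 to 0.61 with 50 people and 0.16 to 0.59 with 60. The rule takes no account of this.

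**Step 8: sign.** If the scales ran in opposite directions and the correlation was −0.7 at both levels, the printed rule would pass in 0% of runs and the same rule on |r| in 100%. If the scales run the same way, no problem of sign arises.

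**The case against.** **The sign.** It is tempting to infer that the rule has the wrong sign, because a symptom score should fall as health or satisfaction rises. The documents do not establish this. They give no scoring direction for EQ-5D-3L or for the TSQM side-effects domain. They label the daily scale both symptoms and quality of life, although the legend to Figure 1 in Protocol section 1.2 does imply that a higher score means more symptoms. The word strong in the SAP can also be read as referring to magnitude. What stands is that the direction is undefined.

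**Other evidence on the score.** A reader might infer that this is the only planned evidence on the instrument. It is not. Protocol section 3.2 plans cognitive interviews and scale refinement, and Protocol Appendix 2 reports daily scoring for a week against an EQ-5D-style format. That exercise used hot and cold ratings in 16 unmedicated healthy volunteers, so it says little about symptom change on tablets, but it exists.

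**The level.** A same-month correlation is not purely between people. Treatment order is randomised for each participant, so in any month people are on different treatments and treatment-driven change enters. This is correct, and Step 3 allows for it. It makes the statistic mixed rather than irrelevant.

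**The scenarios.** They are assumed, and the false pass disappears at low between-person shares. It also requires aligned scoring or a rule on |r|: with opposed scales and the rule read literally, such a score would fail. The false pass and the sign failure therefore belong to different readings and should not be added together.

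**Consequence.** Nothing in SAP sections 6.1 and 6.1.1 makes Hypothesis 2 conditional on this check. That stands in full.

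**Conclusion.** The concern holds as a low-cost improvement. As the plan most naturally reads, convergent validity is judged by a statistic that mixes stable between-person differences with within-person change, while the endpoint uses only the latter.

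Under the assumed values the rule can pass a score with no within-person tracking (monthly r about 0.56 at a 70% between-person share). That needs a share of about one half or more at r_b = 0.8, together with aligned scoring or a magnitude rule. It can narrowly miss a score that tracks change well (about 0.38 at a 70% share), which at those correlations needs a share above about two thirds. Neither outcome can be called likely from the documents, because they give none of the quantities involved.

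On sign, the supportable finding is a missing specification, not an error. The check does not govern the primary analysis; what it affects is how far the new score can be claimed to follow change within a person.

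**What to change.** In SAP section 10:

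1. Add a person-mean-centred (repeated-measures) correlation. Subtract each participant's own mean from their monthly symptom scores and from their monthly questionnaire scores, correlate the deviations, and give a confidence interval by resampling participants. Base any claim that the score tracks change within a person on this statistic.
2. Keep the planned same-month correlations and invariance models, labelled as mixed or between-person evidence, and say how the 12 monthly values are combined.
3. Do not carry the 0.4 cut-off over to the within-person statistic without a justification. Reporting the estimate and its interval is enough.
4. State the direction of the daily score and of each questionnaire, name the EQ-5D-3L score used, and apply the criterion in the expected direction. Use one label for the daily scale throughout.
5. For the TSQM side-effects domain, state how the four no-medication months are handled, or restrict that comparison to tablet months.

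The cost is SAP wording and a few lines of code on data the trial already collects. The downside is that within-person correlations may be smaller than same-month ones, so the validity claim may come out less favourable.
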